2.0 INTRODUCTION

2.1 Study Rationale

OP0201 metered dose inhaler (MDI) (referred herein simply as OP0201) is a novel, intranasal drug-device surfactant product being developed by Novus Therapeutics, Inc., for the treatment and prevention of otitis media (OM). To date, there is no drug product that has been approved to treat or prevent OM.

OP0201 is comprised of a 20:1 fixed combination of dipalmitoylphosphatidylcholine (DPPC; a phospholipid surfactant) and cholestryl palmitate (CP; a neutral phospholipid spreading agent) suspended in propellant (HFA 134a). There are no other ingredients (ie, no excipients, no fillers) in the formulation other than the active ingredients and the propellant. None of these ingredients contain any animal or human derivatives. Both DPPC and CP are highly endogenous surfactants in humans, including the Eustachian tube (ET), nasopharynx, and respiratory system.

The drug product will be delivered as a local treatment through each nostril using a metered dose inhalation device. It will be sprayed directly backwards into each nostril by way of the anterior nostrils (not upwards towards the osteomeatal opening to the maxillary and ethmoid sinuses as other common intranasal products) towards the lateral wall of the nasal cavity so that the usual nasal mucociliary clearance pathway can facilitate delivery of the drug to the ET.

This Phase 1 safety study is designed to evaluate the safety and tolerability of daily intranasal OP0201 use for 14 consecutive days in 30 healthy adults. The study will be randomized, double-blind, placebo-controlled, parallel-group, and includes a dose-escalation cohort design with evaluation of 30 mg per day (Cohort A) and 60 mg per day (Cohort B) of OP0201.

For more information about OP0201, please refer to the most recent Investigator's Brochure (IB).

2.2 Background

The ET is a compliant liquid-lined tube between the middle ear (ME) and the nasopharynx. The ET serves 3 major physiologic functions: 1) ventilation of the ME to maintain ambient air pressure, 2) clearance of fluid from the ME to nasopharynx, and 3) protection of the ME ([Chandrasekhar and Mautone, 2004](#); [Siebert and Danner 2006](#)). In children, ET dysfunction resulting in inflammation of the ME, referred to as OM, is often triggered by a viral infection of the upper respiratory system ([Chonmaitree et al, 2008](#); [Thomas et al, 2014](#); [Schilder et al, 2016](#)). Furthermore, the ET of infants and young children are short, floppy, horizontal and function poorly, which makes ME fluid flow more challenging ([Rosa Olivares et al, 2015](#); [Rovers et al, 2004](#)). A viral infection increases mucus production as well as alters the properties of mucus in the nasopharyngeal region, resulting in diminished normal mucociliary clearance by mucosal cells of the ET and nasopharynx and creating inflammation in the area. This causes dysfunction

of the ET leading to negative ME. The presence of viruses and/or bacteria in the ME results in inflammation and build-up of mucus or liquid behind the tympanic membrane (ie, OM). Common forms of OM are acute otitis media (AOM) and otitis media with effusion (OME). Otitis media with effusion is a build-up of mucus/liquid behind the tympanic membrane without symptoms of an ear infection. Often, there are no symptoms of OME; or there are subtle findings (eg, ear rubbing, clumsiness, conductive hearing loss, and disturbed sleep). In contrast, AOM often occurs when bacteria or viruses get trapped in the ME and cause fever, ear pain and active (acute) inflammation. Both AOM and OME are the result of a dysfunctional ET.

Both DPPC and CP are established endogenous components in human nasal passages and ET and are present on the liquid surface of the nasal passage and ET mucosal lining, and the entire respiratory system. Among phospholipid compounds, DPPC is the most hydrophobic and surface active (Notter, 2000; Taeusch et al., 2002). The hydrophobic nature of DPPC causes it to spread very slowly over an aqueous surface. However, in the presence of a spreading agent (ie, CP), phospholipids easily “spread” along a surface pressure gradient of mucosal lined lumens (Colacicco and Basu, 1977; Notter, 2000). Together these 2 active ingredients effectively absorb to the mucosal air-liquid interface and reduce the interfacial surface tension of the ET, which reduces passive opening pressure required to open the ET. In other words, DPPC + CP promotes ‘de-sticking’ and restoration of physiologic activity of the ET. Thus, the 3 major ET physiologic functions (clearance of fluid from the ME to nasopharynx, ventilation of the ME to maintain ambient air pressure, and protection of the ME) are restored. In turn, it is hypothesized that acute symptoms of OM will be relieved by providing a physiologic opening to the closed ME space, and, with repeat usage, future OM episodes will be prevented. The surfactant is delivered locally to the nasopharyngeal tissue via the nostrils to reduce the local surface tension and pressure that is preventing the ET from functioning normally. By restoring ET functionality, OPO201 facilitates normal ventilation of the ME, which in turn corrects the negative ME pressure that causes otalgia (ear pain) in patients with AOM. Restoring ET function facilitates ME drainage, which in turn may resolve hearing difficulties in patients with OME. In patients at risk of developing OM, delivering the surfactant to the nasopharyngeal tissue via the nostrils may prevent ET dysfunction and in turn prevent AOM and/or OME.

2.3 Benefit/Risk Assessment

As this study is being conducted in healthy human subjects, a health benefit to the subject is not expected.

OP0201 has not yet been evaluated in humans in controlled clinical studies. Thus, information regarding expected adverse events (AEs) from controlled clinical studies is unknown. However, a limited amount of data from 9 human cases exposed to 1 or more doses of other formulations of the investigational drug product (200:1 and 16:1 ratio) is available (see Section 5.2.1 of the IB for further information).

Surfactants, such as DPPC and CP, are components in several pharmaceutical products that have received approval by health authorities, including United States (US) Food and Drug Administration (FDA) and many European Union (EU) countries, (eg, Alveofact[®], Curosurf[®], Infasurf[®], and Survanta[®]) as intratracheal treatment of premature infants with respiratory distress syndrome (RDS). The propellant excipient, HFA-134a, is used in approved metered dose oral inhalers (eg, Proventil HFA[®] [albuterol], Aerospan[®] [flunisolide]) and intranasal inhalers (eg, QNASL[™] [beclomethasone]) containing active pharmaceutical agents for the management of asthma and chronic obstructive pulmonary disease. The device used to deliver OP0201 to the nostrils is similar to devices utilized in the delivery of other approved inhaled metered dose products.

The Sponsor will immediately notify the Principal Investigator if any additional safety or toxicology information becomes available during the study.

3.0 OBJECTIVES AND ENDPOINTS

Table 4 Study Objectives and Endpoints

Objectives	Endpoints
Primary	
 To evaluate the safety and tolerability of OP0201 30 mg per day (given as 2 sprays per nostril 3 times a day [TID] for 14 consecutive days) and OP0201 60 mg per day (given as 4 sprays per nostril TID for 14 consecutive days) compared to 0 mg placebo (HFA-134a only) administered in a similar parallel-group fashion TID for 14 consecutive days in healthy adult volunteers.
Secondary/Exploratory	
 Adverse events, otoscopy, tympanometry, nasal and epipharynx endoscopy, University of Pennsylvania Smell Inventory Test (UPSIT) olfactory test, audiology pure tone hearing test, triplicate 12-lead electrocardiogram, physical examination, vital signs, and clinical laboratory tests. Maximum baseline adjusted serum concentration (C_{max}) of DPPC on Day 14. Time to maximum concentration (t_{max}) of DPPC on Day 14. Maximum baseline adjusted serum concentration (C_{max}) of CP on Day 14. Time to maximum concentration (t_{max}) of CP on Day 14. Additional parameters may be calculated, if appropriate.

4.0 STUDY DESIGN

4.1 Overall Design

This is a randomized, double-blind, placebo-controlled, parallel-group, dose-escalation study in healthy volunteers to evaluate the safety and tolerability of OP0201 administered intranasally 3 times a day (TID) using a MDI compared to a matching placebo (HFA-134a minus active ingredients) administered intranasally TID using a MDI for 14 consecutive days (see [Figure 1](#) for the study schematic). The plan is to enroll up to 30 subjects at 1 study center in the US. Two dose cohorts are planned (Cohort A and Cohort B; N=15 per cohort, see Cohort Dosing below, [Table 5](#)). Within each cohort, subjects will be randomized in a 4:1 ratio to receive either OP0201 or placebo. After all subjects in Cohort A have completed the Day 14 visit, a Safety Review Committee (SRC) will review all the blinded safety data to determine whether the doses administered are safe and well tolerated. The SRC will make a recommendation to escalate to the next cohort (Cohort B) or not.

Table 5 Dose Cohorts and Dose Regimen

Cohort	Dose Regimen	Cohort Dose Allocation		Total Subjects in Each Cohort	Total Subjects Per Dose Group
		Per Day Total Dose (mg)	Cumulative Total Dose (mg)		
A	2 sprays per nostril TID x 14 days	OP0201 (30 mg) ^a Placebo (0 mg)	OP0201 (420 mg) ^a Placebo (0 mg)	15	N=12 (OP0201) N=3 (Placebo)
B	4 sprays per nostril TID x 14 days	OP0201 (60 mg) ^a Placebo (0 mg)	OP0201 (840 mg) ^a Placebo (0 mg)	15	N=12 (OP0201) N=3 (Placebo)

a 2.5 mg per spray

N = number of subjects; TID = 3 times a day

Potential subjects will be screened for eligibility during a screening period (Days -28 to -1). Eligible healthy volunteers will be admitted to the study center on Day -1 and be randomized on Day -1. Subjects will remain resident at the study center until after all the Day 15 assessments have been completed (see [Table 3](#) for the Schedule of Assessments [SoA]), with a study exit visit at Day 21.

Study treatment will be administered to the subjects by study center staff TID for 14 days while resident at the study center.

The estimated duration of participation in the study for each subject is up to 54 days: Screening (Days -28 to -1), treatment (Day 1), 16-day residency (Day -1 to Day 15 with safety assessments at Days 4, 8, 14 and 15), study exit (Day 21 [+5 days]). No efficacy assessments will be performed for this study.

4.2 Scientific Rationale for Study Design

This study is designed to evaluate the safety and tolerability of OP0201 versus placebo in healthy volunteers using a well-designed, scientific method for comparing treatments.

The study design is that of a well-controlled clinical study that includes elements necessary for a valid evaluation of safety and tolerability of repeat OP0201 doses for 14 days. The study is randomized, and treatment is masked for the Investigator, study center personnel, and the subjects to minimize bias. A parallel-group design eliminates possible confounding effects that are inherent in other study designs (eg, cross over).

The placebo (HFA-134a minus active ingredients) was selected to evaluate the comparative safety profile of OP0201 versus a non-drug containing control arm. HFA-134a was chosen as the placebo control since it is the propellant used in the OP0201 formulation. HFA-134a is used as a propellant in other marketed nasal products and has a good safety and tolerability profile in patients suffering from perennial allergic rhinitis ([Weber et al, 2006](#)).

The current study is designed to show that OP0201 is safe and well tolerated compared to the placebo ([FDA Drug Study Designs - Information Sheet](#)).

4.3 Justification for Dose

The US FDA has agreed that animal toxicology studies with OP0201 are not needed to proceed with evaluating this treatment in humans, since the active ingredients are present in other marketed products and the active ingredients are highly endogenous to the human respiratory tract. The composition of OP0201 is designed to maximize the lowering of the mucosal surface tension. Safety and proof of concept results from animal pharmacology studies are considered supportive of the formulation intended for human use. Across several nonclinical pharmacology studies, the beneficial effects of OP0201 were consistently better than those of no treatment and treatment with placebo alone (HFA-134a minus active ingredients) (see IB, Section 4, for more details). A multiple day dose of 20 mg twice daily was given to chinchillas for 10 days. The total exposure was calculated at 400 mg over 10 days; approximately 800 to 1100 mg/kg for a chinchilla weighing 0.35 to 0.5 kg ([Chandrasekhar and Mautone, 2004](#)). No AEs were observed in any of the animal studies.

The clinical safety and tolerability of OP0201 (DPPC:CP 20:1 [weight/weight] (w/w), manufactured by Novus Therapeutics, Inc.) for human use is further guided by a limited amount of data from 9 human cases exposed to 1 or more doses of other formulations of the investigational drug product (200:1 w/w and 16:1 w/w). A total of 8 cases were exposed to DPPC:CP 16:1 w/w in HFA-134a with each 0.1 mL spray delivering 2.5 mg active ingredient. One case exposed to DPPC:CP 200:1 w/w in HFA-134a, with each 0.1 mL spray delivering 5 mg of active ingredient (see IB, Section 5.2.1).

This Phase 1 safety study is designed to evaluate the safety and tolerability of OP0201 in 30 healthy volunteers. The dosing regimen for each of the 2 dose cohorts to be evaluated in this study are defined in [Table 5](#). A TID dosing exceeds the anticipated once daily or maximum twice daily dosing interval that may be evaluated in patients in future studies. Because of the endogenous nature of the active ingredients, pharmacokinetic (PK) profiles cannot be obtained to guide on dose or dosing interval. Furthermore, the treatment is anticipated to have a local effect on the ET, and thus systemic plasma levels wouldn't necessarily have relevance. The maximum number of sprays of 4 per nostril to be evaluated in this Phase 1 study also exceed the anticipated practical maximum number of sprays of 2 per nostril that will be evaluated in patients in future studies. The dose, number of sprays, and dosing interval for this Phase 1 study were chosen because they are expected to exceed the total daily dose for dosing schema that will be tested in patients in future studies, and thus establish a high safety threshold.

The surfactant active ingredients of OP0201 are endogenous to human nasal and respiratory mucosal surfaces. Additionally, surfactants have been approved for topical administration via the trachea to infants with RDS with a long history of safety and tolerability at much higher exposure levels on a mg/kg basis than proposed herein (see IB, Section 4.1.5, Table 5). Thus, in this study daily repeat maximum doses of 20 mg TID for 14 days are to provide an estimated total exposure of 840 mg over 14 days; approximately 12 mg/kg for a human weighing 70 kg.

Rationale for Route of Administration

The target end organ for the study treatment is the ET, which exits the ME and resides in the nasopharynx. In adults, the nasal passage extends about 10 to 14 cm from the nostrils to the nasopharynx ([Reznik, 1990](#)). Access to the ET is via the nostril. Because of the physical location of the ET in the nasopharynx, the angle of the delivery of the investigational product (IP) in the nostril is in a horizontal direction towards the back of the nose, not vertical towards the sinus cavities (not 'up' into the nose) as for other nasal inhaled products. The IP is delivered using a MDI; thus there is no need for the user to sniff or breathe in a certain way for the IP to reach the ET.

4.4 End of Study Definition

A subject is considered to have completed the study if he/she has completed all phases of the study including the last visit.

The end of the study is defined as the date of the last visit of the last subject in the study.

4.5 Dose-Escalation Criteria

After all subjects in Cohort A have completed the Day 14 visit, a SRC will review all the blinded safety data to determine whether the doses administered are safe and well tolerated and to make a recommendation to escalate to the next cohort (Cohort B) or not.

4.6 Study Stopping Criteria

4.6.1 Stopping Criteria for Individual Subjects

Study treatment for any individual subject will be stopped if the subject experiences a serious adverse event (SAE) or a clinically significant possibly drug-related related AE, which in the opinion of the study physician, Principal Investigator, or Sponsor's medical representative, warrants discontinuation of the study for that subject's wellbeing. See Section [7.1](#) for general discontinuation procedures.

Any female subject who becomes pregnant while participating in the study will be withdrawn from the study.

4.6.2 Criteria for Stopping Dose-Escalation

Dose-escalation will be stopped if any of the study stopping rules are met.

4.6.3 Criteria for Stopping the Study

If 1 or more subjects experience drug-related SAEs or 2 or more subjects experience any drug-related severe AEs, the study will be stopped.

If any of the following scenarios occur with a reasonable possibility of a causal relationship with the study treatment, the study will be stopped:

- ≥ 1 subject experiences SAEs considered to have a reasonable possibility of relationship to the study treatment.
- ≥ 2 subjects experience non-tolerable AEs that are considered to have a reasonable possibility of relationship to the study treatment.
- ≥ 1 subject receiving study treatment fulfills Hy's Law defined as alanine aminotransferase (ALT) $>3 \times$ the upper limit of normal (ULN) and bilirubin $>2 \times$ ULN in the absence of significant increase in alkaline phosphatase (ALP) and in the absence of an alternative diagnosis that explains the increase in total bilirubin, to be assessed from the first administration of study treatment up to and including follow-up.
- ≥ 2 subjects who receive study treatment have >2 ULN of either ALT, bilirubin, or ALP.
- ≥ 2 subjects who receive study treatment have a QTc prolongation defined as QTcF >500 ms, or an increase of QTcF >60 ms above baseline on the 12-lead electrocardiogram (ECG), confirmed (persistent for >5 minutes) on repeated 12-lead ECGs.

5.0 STUDY POPULATION

Prospective approval of protocol deviations to recruitment and enrollment criteria, also known as protocol waivers or exemptions, are not permitted.

Healthy volunteers are those who are otherwise healthy and who meet the eligibility criteria below.

5.1 Inclusion Criteria

Healthy volunteers are eligible to be included in the study only if all of the following criteria apply:

1. Subject has signed an informed consent form (ICF) before any study-specific procedures are performed.
2. Male or female healthy volunteers aged 18 to 50 years at the time of signed informed consent.
3. Able and willing to follow study instructions (including compliance with daily study treatment administration) and likely to complete all required study visits as assessed by the Investigator's judgement.
4. Body mass index of 18 to 30 kg/m² (inclusive) and a minimum body weight of 50 kg at Screening.
5. Female subjects must agree to use an acceptable method of contraception (see [Appendix 6](#) for pregnancy considerations and contraceptive requirements).
6. Female subjects who are of childbearing potential must have a negative urine pregnancy test result at Screening and Day -1 prior to randomization.
7. Male subjects must agree to use contraception as detailed in [Appendix 6](#) of this protocol during the treatment period.
8. Subjects must agree to refrain from immersing their head fully under water (eg, swimming, diving) from the time of signed informed consent until after the study exit visit (Day 21).
9. Physiologic tympanogram classified as Type A (normal) by the Investigator or designee.

5.2 Exclusion Criteria

Subjects are excluded from the study if any of the following criteria apply:

1. History or presence of significant medical condition or a clinically significant abnormal finding, as determined by the Investigator. This includes study screening results from:
 - Medical history
 - Physical examination
 - ENT examination (ear history, otoscopy, tympanogram, nose and epipharynx endoscopy)
 - University of Pennsylvania Smell Inventory Test (UPSIT) olfactory test
 - Audiology pure tone hearing test
 - ECG
 - Vital signs measurements
 - Clinical laboratory tests
2. Presence of a clinically significant abnormal olfactory test finding at Screening defined as a total UPSIT score <35 (for females) and <34 (for males).
3. Current diagnosis of Sleep Apnea.
4. Clinically significant ear disorder/disease currently or within 6 weeks prior to Screening.
5. History of tympanostomy tubes in one or both ears within 1 year prior to Screening.
6. Upper respiratory tract infection or pharyngitis currently or within 6 weeks prior to Screening.
7. Allergy or sinus conditions (eg, sinusitis, non-specific nasal inflammation) currently or within 6 weeks prior to Screening.
8. Clinically relevant blockage of one or both nasal passages, in the Investigator's opinion.
9. Gastroesophageal reflux disease currently or within 6 weeks prior to Screening.
10. Smoker (eg, cigarettes, vapor) or tobacco or nicotine use within the last 48 weeks prior to Screening and positive urine cotinine test results at Screening or Day -1 prior to randomization.
11. Females with positive urine pregnancy results at Screening or Day -1 prior to randomization.
12. Females who are nursing or planning a pregnancy during the study.
13. Females of childbearing potential who are not willing to use an acceptable method of contraception during the study (see [Appendix 6](#)).

14. Symptomatic herpes zoster within 12 weeks prior to Screening.
15. Lymphoma, leukemia or any malignancy within the past 5 years except for basal cell or squamous epithelial carcinomas of the skin that have been resected with no evidence of metastatic disease for 3 years.
16. Breast cancer within the past 10 years.
17. Live vaccine within 30 days prior to Screening, or plans to receive such vaccines during the study.
18. Evidence of craniofacial anomalies (eg, cleft palate, Down's Syndrome).
19. Disorders with decrease mucociliary clearance or higher viscosity of the mucous (eg, cystic fibrosis, primary ciliary dyskinesia, Kartagener's syndrome).
20. Use of any medication (either topically or systemically) for a condition related to the ear or nose currently or within 12 weeks prior to Screening.
21. Use of medications with known vasoconstrictive properties (eg, local anesthetics, decongestants) currently or within 2 weeks prior to Screening.
22. Use of medications with known anti-cholinergic side effects (eg, antihistamines, antiemetics, muscle relaxants, antidepressants) currently or within 6 weeks prior to Screening.
23. Within 7 days prior to the first study treatment administration, use of any prescription drug (except oral contraceptive), nicotine-containing product (including nicotine patch), over-the-counter drug, herbal supplement, vitamin, or dietary supplement with the exception for occasional use of acetaminophen not exceeding 3 grams per day.
24. Regular alcohol consumption within 24 weeks prior to Screening defined as an average weekly intake of >21 units for males and >14 units for females; 1 unit is equivalent to 8 g of alcohol (a half pint [approximately 240 mL] of beer, 1 glass [approximately 125 mL] of wine or 1 measure [approximately 25 mL] of spirit).
25. History of drug abuse or positive drug screening test at Screening or Day -1 prior to randomization (see [Table 8, Appendix 3](#)).
26. Known allergy or sensitivity to the study treatment or any of its components.
27. Exposure to 3 or more new chemical entities within 12 months prior to Screening.
28. Investigator and study center personnel directly affiliated with this study and/or their immediate families (defined as spouse, significant-other, parent, child or sibling, whether adopted or biologic).

29. Persons employed by the Sponsor or Investigator.
30. Persons held in an institution by legal or official order.
31. Concurrent enrollment in an investigational drug or device study other than the research pertaining to OP0201, or participation in such a study within 30 days of Screening.
32. Subject has a condition or is in a situation which, in the Investigator's opinion, may put the subject at significant risk, may confound the study results, or may interfere significantly with the subject's participation in the study.

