6.5 Concomitant Therapy

Any medication or vaccine (including over-the-counter or prescription medicines, vitamins, and/or herbal supplements) that the subject is receiving at the time of enrollment (within 7 days before the time of enrollment) or receives during the study must be recorded on the electronic case report form (eCRF) along with:

- Reason for use.
- Dates of administration including start and end dates.
- Dosage information including dose and frequency.

The Medical Monitor should be contacted if there are any questions regarding concomitant or prior therapy.

Subjects must abstain from taking prescription or nonprescription drugs (including vitamins and dietary or herbal supplements) within 7 days or 5 half-lives (whichever is longer) before the start of study treatment until completion of the study exit visit (Day 21). In the case of medications (either topically or systemically) for a condition related to ear or nose, subjects must abstain from taking these within 12 weeks before the start of study treatment, or 2 weeks in the case of medications with known vasoconstrictive properties (eg, local anesthetics, decongestants), or 6 weeks in the case of medications with known anti-cholinergic side effects (eg, antihistamines, antiemetics, muscle relaxants, antidepressants). An exception is that women of childbearing potential (WOCBP) may take protocol defined acceptable oral contraceptives.

Acetaminophen, at doses of \leq 3 grams/day, is permitted for use any time during the study. Other concomitant medication may be considered on a case-by-case basis by the Investigator in consultation with the Medical Monitor (if required).

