7.5. BASELINE

Baseline is defined as the last scheduled non-missing measurement taken prior to dosing and will

Document: Statistical Analysis Plan
Author: [REDACTED]

Version Number:
Version Date:

2.0
03APR2019

correspond to: Screening assessment for clinical laboratory; Day -1 assessment for Vital Signs; Day 1 pre-dose assessment for ECG in Cohort A, and the average of the mean triplicate ECG assessments at Day 1, 60 minutes pre-dose and Day 1, 30 minutes pre-dose for ECG in Cohort B; Screening assessment for Physical Examination; Day -1 assessment for Otoscopy, Tympanometry, and Nasal and Epipharynx Endoscopy ; and Screening assessment for University of Pennsylvania Smell Inventory Test (UPSIT) Olfactory test, and Audiology Pure Tone hearing test. However, if a subject is missing the planned baseline collection then the last non-missing evaluation prior to dosing (scheduled or unscheduled), if available, will become the baseline value.

For PK assessments, baseline serum concentration is defined as the mean of the two predose serum concentrations observed in samples collected on Day 1 prior to the first dose. If one predose sample is missing, the other Day 1 predose concentration will be used for baseline correction.

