10. DISPOSITION AND WITHDRAWALS

All entered subjects as defined in the Entered Analysis Set will be accounted for in this study. Subject disposition will be tabulated by cohort and treatment for number of subjects entered, randomized, treated, prematurely withdrew, completed study, and for each reason of premature withdrawal from the study along with the associated percentages. The percentages for the reason of withdrawal for screen failure subjects will be based on the entered set, whereas it will be based on safety set for treated subjects. The tabulation will also be presented for all active treated subjects, all placebo treated

Document: Statistical Analysis Plan
Author: [REDACTED]

Version Number: 2.0
Version Date: 03APR2019

[REDACTED]
[REDACTED]

subjects, and for all subjects combined from both cohorts, irrespective of treatment received, as Overall.

A listing will present dates of completion or early withdrawal and the reason for early discontinuation, if applicable, for each subject. Screen failure subjects will be listed indicating the primary reason of screen failure and will be included in disposition summary tabulations.

Listings of inclusion/exclusion criteria responses, study eligibility during screening and Day -1, and study treatment administration date and times will be provided.

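### An ear, respiratory or sinus illness that starts after Screening and clears before Day -1 meets no fixed exclusion, while the smell and hearing baselines date from Screening

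*Protocol*

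**What the plan says.** Three criteria in Protocol Section 5.2 share one window:

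- Criterion 4: "Clinically significant ear disorder/disease currently or within 6 weeks prior to Screening".
- Criterion 6: "Upper respiratory tract infection or pharyngitis currently or within 6 weeks prior to Screening".
- Criterion 7: "Allergy or sinus conditions (eg, sinusitis, non-specific nasal inflammation) currently or within 6 weeks prior to Screening".

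Protocol Section 4.1 places Screening anywhere from Day -28 to Day -1. Table 3 repeats the inclusion/exclusion check on Day -1, and SAP Section 10 accordingly lists "study eligibility during screening and Day -1".

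SAP Section 7.5 takes as baseline the "Screening assessment for University of Pennsylvania Smell Inventory Test (UPSIT) Olfactory test, and Audiology Pure Tone hearing test". Table 3 repeats neither test before dosing: the next UPSIT is on Day 8 and the next hearing test on Day 14. Otoscopy, tympanometry and nasal/epipharynx endoscopy are repeated on Day -1 and take their baseline there.

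Under Protocol Section 8.2.8, a UPSIT change from normal to abnormal is recorded as an AE. SAP Section 17.5 also counts it in a shift table. An illness arising between consent and first dose is recorded as a pre-treatment AE (Protocol Section 8.3.1), which SAP Section 17.1 shows in listings only.

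**The concern.** The look-back is anchored to Screening, but exposure starts up to four weeks later. The more recent illness can pass while the older one excludes, which is the reverse of what a washout is for. Other criteria carry an anchor nearer to dosing: 10, 11 and 25 refer to Screening or Day -1, and 23 counts back from the first dose.

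At stake is the reading of two primary safety endpoints. An illness in the gap falls between the baseline and the first post-dose smell or hearing test, so any residual effect would appear as a post-treatment change. UPSIT leaves little room for this: entry needs at least 35 (females) or 34 (males), and one point below that is abnormal. The groups are small and the analysis is descriptive, so one or two such changes would show in the tables.

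**Working it through.** **1. Day count (no Day 0).** The plan's own figure reproduces: 28 screening days + 26 days (Day 21 + 5) = 54 days, the stated maximum participation.

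- Day -28 to first dose on Day 1: 28 days.
- Day -28 to the Day -1 check: 27 days.
- Age of the UPSIT baseline: up to 35 days at Day 8 and 41 days at Day 14.
- Age of the hearing baseline: up to 41 days at Day 14.

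**2. Two illnesses compared, with Screening on Day -28.**

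- A cold that ended 5 weeks before Screening ended 35 + 28 = 63 days before dosing. Criterion 6 excludes it.
- A cold from Day -14 to Day -8 ended 8 days before dosing. It is neither before Screening nor current on Day -1, so criterion 6 does not exclude it.

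The latest such illness clears by Day -2, two days before dosing. One still present on Day -1 is excluded as current.

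**3. Drug windows.** Criterion 23 bars most drugs in the 7 days before first dosing. For ear and nose medicines, Protocol Section 6.5 says "subjects must abstain from taking these within 12 weeks before the start of study treatment", with 2 weeks for vasoconstrictive and 6 weeks for anti-cholinergic drugs. These rules catch many treated colds. They miss an untreated one, or one treated only with permitted acetaminophen. Criteria 20 to 22 anchor the same drug windows to Screening, so they and Section 6.5 need reconciling.

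**4. Weight of one event.** Active group: 1/12 = 8.3 percentage points. Placebo pooled across cohorts (SAP Section 7.2): 1/6 = 16.7 percentage points.

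**5. Frequency (assumed; the documents give no rate).** Take r colds per person-year, each lasting 7 days, and a gap of g days from Screening to Day -1. To start and clear within the gap, a cold must begin in the first g - 7 days:

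P = 1 - exp(-r × (g - 7)/365)

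| Gap | r = 2 | r = 3 | r = 4 |
|---|---|---|---|
| 7 days | 0% | 0% | 0% |
| 14 days | 3.8% | 5.6% | 7.4% |
| 27 days | 10.4% | 15.2% | 19.7% |

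Central case: 1 - exp(-3 × 7/365) = 5.6%, and 30 × 0.056 = 1.7 subjects. At the upper end, 30 × 0.197 = 5.9 subjects. These figures precede any removal by the drug windows or Investigator discretion. They count illnesses, not smell or hearing changes.

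**The case against.** The best defence is that the plan is not without cover, and most of it stands.

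- **Discretion.** Criterion 32 lets the Investigator exclude a subject whose situation may confound the results, and criterion 1 covers significant history or findings. Both can be applied on Day -1. What is missing is a fixed rule, not all protection.
- **Recording and causality.** The illness would be listed as a pre-treatment AE, and Protocol Appendix 4 has the Investigator weigh alternative causes. A smell AE need not be judged related to treatment. It would still count as treatment-emergent and as a shift.
- **Mechanism.** Protocol Section 2.2 says that middle-ear inflammation in children "is often triggered by a viral infection of the upper respiratory system", acting through nasopharyngeal mucus and the Eustachian tube. Tympanometry covers that function and is renewed on Day -1. No figure in the documents shows smell or hearing loss persisting after a cleared cold with normal Day -1 findings.
- **Screening capacity.** The 60 to be screened already assumes one failure per enrolled subject, and Section 5.4 bars rescreening. The Synopsis does, however, allow additional screening.

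Two stronger readings are tempting. A reader might infer that a seasonal wave striking one of the sequential cohorts would mimic a dose effect. The documents give no enrolment dates, the amendment and SAP dates do not establish them, and placebo is randomized within each cohort. A reader might also count every cold starting in the gap, which at 4 a year over 27 days gives 1 - exp(-4 × 27/365) = 25.6%. That includes colds still present on Day -1, which are excluded.

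**Conclusion.** The gap in the wording is real but narrow. Criteria 4, 6 and 7 leave up to 27 days between Screening and the Day -1 check in which an illness can come and go without meeting a fixed exclusion. Only UPSIT and audiometry carry a baseline from before that interval.

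On the assumed rates, about 0 to 20% of subjects would have such a cold, centrally 5.6% or 1.7 of 30. The share who would then show a smell or hearing change is unknown and smaller. The result depends on the assumed rate, the 7-day duration and the actual spread of screening-to-admission gaps, none of which the documents state. Randomization within cohort means that no arm is systematically favoured; the risk is a chance event misread in small groups. This is an optional, cheap improvement, not a threat to the study's validity.

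**What to change.** In criteria 4, 6 and 7, replace the present window with: *within 6 weeks prior to Screening or at any time from Screening to Day -1*. Apply it at the Day -1 eligibility check that Table 3 already schedules; no new procedure is needed.

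The cost is one phrase in three criteria and a few more Day -1 exclusions. Because those subjects may not be rescreened, slightly more than 60 may have to be screened, which the Synopsis permits. The change does not renew the smell and hearing baselines, which could still be up to 28 days old at first dosing. It removes the subjects in whom one of these illnesses fell between baseline and dosing.
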